10.4.3 Safety Analyses

Safety will be assessed by reporting the grades of toxicity and the type of toxicity observed for all patients and summarizing data using the descriptive statistics, including mean, standard deviation and confidence intervals.

10.4.4 Planned Interim Analyses

Two-stage sequential enrichment design will be used for this trial. In the first stage, we will enroll 9 patients with *RELA*-fusion ependymomas (Cohort 1) to test for clinical activity of marizomib. If 4 or more patients are progression free at 6 months, we proceed to stage 2; otherwise we terminate the trial and conclude that marizomib is not effective. At stage 2, we will enroll 32 patients with non *RELA*-fusion ependymomas (Cohort 3 and 4). From Cohort 3, if 9 or more of 16 patients are progression free at 6 months, we claim that marizomib is promising for treating both *RELA*-fusion and non *RELA*-fusion ependymoma; otherwise, we claim that marizomib is promising for treating *RELA*-fusion, but not for non *RELA*-fusion ependymoma. As above, PFS-6 for Cohort 4 will also be measured in patients with non-*RELA* fusion ependymoma that has been extensively treated. These data will be compiled as preliminary data regarding efficacy of marizomib as a salvage regimen for patients with heavily pretreated non-*RELA*-fusion ependymoma.

10.4.5 Exploratory Analyses

Determination of RELA gene fusion status and expression of NF- κ B pathway to correlate with clinical course of ependymoma patients treated with Marizomib using Spearman correlation and regression analysis; the levels will be compared between responders and non-responders using an exact Wilcoxon rank sum test

Impact of baseline somatic genomic profile of ependymoma on clinical response to Marizomib. The number of somatic mutations, copy number alterations and fusions obtained for each patient will be compared between responders and non-responders. This will be done using either a Fisher's exact test, Cochran-Armitage trend test, or exact Wilcoxon rank sum test depending on the distributions of values.

Regression analysis will be further used to investigate the relationship between these covariates and clinical response.

Determination of single nucleotide polymorphisms from germline DNA to correlate with CNS adverse events will be established using an exact Wilcoxon rank sum tes.

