5.3.2 Pharmacogenomic Studies (Cohort 1 only)

One blood sample per patient will be collected from subjects enrolled in Cohort 1 for pharmacogenetic studies to analyze the genomic DNA and assess genotype of the most relevant drug metabolizing enzymes and transporters (DMET). DNA will be analyzed on a DMET Plus (Affymetrix) genotyping platform that tests for 1,936 genetic variations in 231 drug disposition genes, including 47 CYP (phase I metabolism) genes, 13 non-CYP (phase I metabolism) genes, 78 phase II metabolizing genes (including UGTs), 63 transporters, 4 genes involved in facilitation of drug transporters, 9 genes involved in global regulation of drug metabolizing/transporting proteins, 4 drug binding proteins, and 4 drug targets. The DMET data will be correlated with response and/or toxicity.

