6.3.1 Disease Parameters

Measurable Disease: Bi-dimensionally measurable lesions with clearly defined margins by MRI. All tumor measurements must be recorded in millimeters (or decimal fractions of centimeters). Based on RANO criteria **Table 6** [26].

Objective Status: To be recorded at each evaluation: If there are too many measurable lesions to measure at each evaluation, choose the largest two to be followed before a patient is entered on study. The remaining lesions will be considered evaluable for the purpose of objective status determination. Unless progression is observed, objective status can only be determined when ALL measurable and evaluable sites and lesions are assessed.

Time to Treatment Failure: From date of registration to the date of first observation of progressive disease, non-reversible neurologic progression or permanently increased steroid requirement (applies to stable disease only), death due to any cause, or early discontinuation of treatment.

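### The somatic-profile analysis in 10.4.5 compares only responders with non-responders and leaves its regression outcome undefined, giving up power that tumour measurements already collected could supply

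*Combined protocol and SAP*

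**What the plan says.** For the baseline somatic profile, section 10.4.5 says "The number of somatic mutations, copy number alterations and fusions obtained for each patient will be compared between responders and non-responders". The test is to be "either a Fisher's exact test, Cochran-Armitage trend test, or exact Wilcoxon rank sum test depending on the distributions of values". It then adds: "Regression analysis will be further used to investigate the relationship between these covariates and clinical response". It does not say whether clinical response is binary, ordinal or a percentage change, and it does not define responder. The natural reading is CR or PR under 6.3.3, where PR needs at least a 50% reduction in the sum of products together with the T2/FLAIR, new-lesion, corticosteroid and clinical-status conditions of Table 6.

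For RELA status and NF-κB expression the same section goes further. These are "to correlate with clinical course of ependymoma patients treated with Marizomib using Spearman correlation and regression analysis", as well as being compared by responder group.

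On the data available, 6.3.1 has lesions measured in two dimensions, 6.3.3 has response re-evaluated every 8 weeks, and 5.1.1 has archival tissue collected from all patients. Section 10.3 limits response evaluability to patients with measurable disease at baseline, at least one cycle of therapy (or objective progression before the end of cycle 1) and a re-evaluation.

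**The concern.** The responder split puts a patient with 45% shrinkage in the same group as a patient who progresses at once. Differences within each group, which may carry much of a biomarker signal, play no part in the named tests. The plan gives no reason for preferring the split here, and it already accepts a rank correlation for NF-κB in the same section.

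At stake is what the trial can learn from the tumour panel under the exploratory objectives in 1.1.3. The design is powered on PFS6 (30% against 60% in 10.1), which counts lasting stable disease as success. No objective response rate is given, so the number of responders could be small. If the trial stops after stage 1, at most 18 patients contribute. A real association would then probably be missed.

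**Working it through.** The plan states no alpha, power or sample size for these analyses, so there is no figure of its own to reproduce.

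**Inputs from the documents.** The largest number of patients is 9 + 9 + 16 + 16 = 50 (3.1.1, 10.2). If the trial stops after stage 1 it is 9 + 9 = 18, and Cohort 1 alone is 9. Section 10.4.5 does not say which cohorts are pooled.

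**Assumptions.** Two-sided 5% level; response rate 10% to 30%; correlation 0.4 or 0.5 between biomarker and depth of response.

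**Step 1: information kept by the split.** For a normally distributed outcome cut so that a proportion p respond, the share of information kept is φ(z_p)² / [p(1 − p)].
- p = 0.10: 0.34
- p = 0.20: 0.49
- p = 0.21: 0.50
- p = 0.30: 0.58
- p = 0.50: 0.64

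More than half is therefore lost only when about 20% or fewer respond. At 30% the loss is 1 − 0.58 = 42%.

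**Step 2: smallest attainable p-value.** With k responders among n patients and no ties, the two-sided exact Wilcoxon minimum is 2/C(n,k). The Fisher minimum found by enumeration is 1/C(n,k) for the small k shown.

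| n | Responders | Wilcoxon minimum | Fisher minimum |
|---|---|---|---|
| 9 | 1 | 2/9 = 0.222 | 1/9 = 0.111 |
| 9 | 2 | 2/36 = 0.056 | 1/36 = 0.028 |
| 18 | 1 | 2/18 = 0.111 | 1/18 = 0.056 |
| 18 | 2 | 2/153 = 0.013 | 1/153 = 0.0065 |
| 50 | 1 | 2/50 = 0.040 | 1/50 = 0.020 |

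With no responders there is nothing to compare at any n. Otherwise, among these three sizes, p < 0.05 is out of reach only with 1 responder among 9 or 18, or with 2 among 9 for Wilcoxon. For one responder, 2/n reaches 0.05 at n = 40, so an evaluable set smaller than that has the same limit on Wilcoxon.

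The chance of at most one responder is (1 − p)ⁿ + np(1 − p)ⁿ⁻¹. For n = 18 it is 45% at a 10% response rate and 10% at 20%. For n = 50 it is 3% at 10%.

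**Step 3: power by simulation.** Biomarker and tumour change were bivariate normal, with 1,500 runs per setting. The exact Wilcoxon test by responder group was compared with Spearman on the full scale. A run with no responders counted as non-significant. Entries are for response rates of 10% / 20% / 30%.

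| n | Correlation | Responder split | Full scale |
|---|---|---|---|
| 50 | 0.4 | 33 / 48 / 59% | 78 / 77 / 80% |
| 50 | 0.5 | 51 / 69 / 77% | 95 / 94 / 95% |
| 18 | 0.4 | 9 / 14 / 20% | 34 / 33 / 34% |
| 18 | 0.5 | 14 / 24 / 31% | 53 / 52 / 51% |

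The gain runs from 34 − 20 = 14 points to 78 − 33 = 45 points.

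**Step 4: a less favourable model.** With tied Poisson counts as the biomarker and 30% of patients tied at the worst rank, power over the same correlations and response rates was 34% to 75% for the split against 74% to 92% at n = 50. At n = 18 it was 8% to 31% against 32% to 50%. The full scale was ahead in every setting.

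**The case against.** The strongest reply is that these analyses are exploratory, that the 50% threshold is the RANO criterion the protocol cites, and that response is more than a size cut. Table 6 also requires stable or falling corticosteroids, no new lesion and stable clinical status, so raw percentage change could credit shrinkage on rising steroids that would fail PR. Best change also depends on how many scans a patient has. All of this stands. It shapes the ranking rule in the fix, but does not make the split the better main analysis. A further objection, that the covariates are counts with ties, is met by step 4.

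A reader might infer several stronger points that the documents do not support:

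- **That tumour size is available for every patient.** Measurable disease is not an entry criterion in 2.1.1, and 10.3 makes it a condition of response evaluability. The responder comparison has the same limit.
- **That the plan uses nothing but a binary outcome.** The regression outcome is undefined and could be graded. The fair criticism is that it must be stated.
- **That most of the information is always lost, or that significance is impossible.** Steps 1 and 2 show that both depend on few responders, and no response rate is given. PFS6 rates do not imply one.
- **That a missed association would be reported as absent.** Nothing in the plan says so.
- **That the DMET data in 5.3.2 are also split.** The text says only that "The DMET data will be correlated with response and/or toxicity"; it names no split and no test. Changing the outcome scale would not help there: with "1,936 genetic variations in 231 drug disposition genes" and 9 patients, a Bonferroni threshold is 0.05/1,936 = 2.6 × 10⁻⁵. The best Wilcoxon p for a two-level genotype is 2/C(9,4) = 2/126 = 0.016.

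**Conclusion.** The point holds as a low-cost improvement to an exploratory analysis. The named tests for the somatic profile rest on a responder split, the regression outcome is not defined, and a graded outcome is already being collected in patients with measurable disease. The loss of power is substantial in every setting tried, but its size depends on assumed correlations and response rates that the documents do not give. The figures also take depth of response as known for all n patients, so a smaller evaluable set would lower power for both methods. At n = 9 alone neither method is adequate: with correlation 0.5 and response rates of 10% to 30%, power is 1% to 9% with the split and 25% to 27% without it. No primary or secondary conclusion of the trial is affected, and the point does not extend to DMET.

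**What to change.** In 10.4.5, for patients evaluable for response under 10.3:

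1. Make the main analysis of each genomic covariate a Spearman correlation or rank regression on best percentage change in the sum of products, and state that this is the outcome of the planned regression.
2. Give the ranking rule. Patients with a new lesion, clinical progression or death before a scan rank worst. Shrinkage seen on increased corticosteroids does not count as improvement, in line with Table 6.
3. Define responder, and keep the responder/non-responder comparison as descriptive.
4. Add a supportive Cox model for PFS, stratified by RELA status, that includes patients with tissue but without measurable disease.

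The cost is SAP wording and a few lines of code, with no new data, visits or patients. Three drawbacks should be stated: the ranking rule involves judgement and must be fixed in advance, best change depends on the number of scans, and the PFS model may reflect prognosis rather than drug effect.

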11 COLLABORATIVE AGREEMENTS

11.1 CRADA

A CRADA (#03205) with Celgene is in place.

12 HUMAN SUBJECTS PROTECTIONS

12.1 RATIONALE FOR SUBJECT SELECTION

This study was designed to include women and minorities, but was not designed to measure differences of intervention effects. Males and females will be recruited with no preference to gender. No exclusion to this study will be based on race. Minorities will actively be recruited to participate.

12.2 PARTICIPATION OF CHILDREN/VIABLE NEONATES

In this study, we are excluding the pediatric population (age <18 years) as no dosing or adverse event data are currently available on the use of marizomib in this group. Viable neonates/children may however be enrolled in Cohort P to study the effects of in utero exposure to the study drug. Data will be collected for up to 1 year after birth. These children may participate in the research under the provisions of 45 CFR Subpart D 46.404 as the research, consisting of data collection on health outcomes, is no more than minimal risk. There is no direct benefit to the child participants.

12.3 PARTICIPATION OF NEONATES OF UNCERTAIN VIABILITY AND NONVIABLE NEONATES

The assessments for this population on the study are limited to data collection, therefore no studies have been conducted for assessing potential risk as they would not be scientifically appropriate in this setting. No interventions are performed on the neonate and risks are limited to data breaches. Persons providing consent will be informed of these risks. Individuals engaged in the research will have no part in determining the viability of the neonate.

12.3.1 Neonates of Uncertain Viability

The purpose of the research, to collect data on the teratogenic effects of study drug exposure, is important biomedical knowledge which cannot be obtained by other means and there will be no added risk to the neonate resulting from the research as data breaches are a risk in the clinical setting as well. In addition,

consent from both parents will be obtained, unless exception criteria in the section **Consent for Children and Neonates** are met.

12.3.2 Nonviable Neonates

Vital functions of the neonate will not be artificially maintained as part of the research, nor will the research terminate the heartbeat or respiration of the neonate. The purpose of the research, to collect data on the teratogenic effects of study drug exposure, is important biomedical knowledge which cannot be obtained by other means and there will be no added risk to the neonate resulting from the research as data breaches are a risk in the clinical setting as well. In addition, consent from both parents will be obtained, unless exception criteria in the section **Consent for Children and Neonates** are met.

12.4 PARTICIPATION OF PREGNANT WOMEN

Pregnant women are excluded from enrolling in Cohorts 1-4 of the study due to the possibly deleterious effects of the study drug. However, participants in cohort 1-4 who become pregnant may be retained on the study. In addition, the pregnant partners of male participants whose pregnancy occurred while during the male's participation in the study may be enrolled in Cohort P.

Pregnant women who were initially enrolled in Cohort 1-4 will be removed from study therapy to minimize the risk (Section **3.8.1**), but they will remain on follow up for safety with procedures limited to those that are generally permitted for pregnant women in the clinical setting. Data collection on the pregnancy represents no more than minimal risk, but it does not hold the prospect of direct benefit to the pregnant woman or to the fetus. However, the purpose of the data collection is the development of important biomedical knowledge that cannot be obtained by any other means. No inducements, monetary or otherwise, will be offered to terminate a pregnancy. No individuals engaged in the research will have any part in decisions as to the timing, method or procedures used to terminate a pregnancy and individuals engaged in the research will have no part in determining the viability of a neonate.

12.5 PARTICIPATION OF SUBJECTS UNABLE TO GIVE CONSENT

Adults unable to provide consent are excluded from enrolling in the protocol. However, it is possible that subjects enrolled in the protocol may permanently lose the capacity to consent for themselves during the course of this study. For subjects that lose the ability to consent due to tumor progression, they will be taken off treatment but will have the opportunity to remain on study in long term follow-up for collection of outcomes for overall survival. If the reason for incapacity is due to a reason other than definitive disease progression and they are felt to be responding to the treatment under study in the opinion of the investigator, they will have the opportunity to continue this therapy.

All subjects \geq age 18 will be offered the opportunity to fill in their wishes for research and care, and assign a substitute decision maker on the "NIH Advance Directive for Health Care and Medical Research Participation" form so that another person can make decisions about their medical care in the event that they become incapacitated or cognitively impaired during the course of the study.

Please see section **12.8.1** for consent procedure.

12.6 POTENTIAL RISKS/ DISCOMFORTS

12.6.1 Study Drug Risks

Marizomib may cause fatigue, dizziness, headache, insomnia, anorexia and gastrointestinal adverse effects. Patients may get cognitive changes, hallucinations and loss of balance which are generally reversible with dose reduction [[20](#), [28](#)]. Myelosuppression is uncommon [[20](#), [28](#)].

12.6.2 Imaging

Scans may include the risks of an allergic reaction to the contrast. Participants might experience hives, itching, headache, difficulty breathing, increased heart rate and swelling. Participants undergoing gadolinium enhanced MRIs may also be at risk for kidney damage.

12.6.3 Research Blood Collection Risks

Risks of blood draws include pain and bruising in the area where the needle is placed, lightheadedness, and rarely, fainting. When large amounts of blood are collected, low red blood cell count (anemia) can develop.

12.6.4 EKG

Other than the minor skin irritation from the electrodes there are no expected risks related to the EKG.

12.6.5 Other Risks

Risks include the possible occurrence of any of a range of side effects which are listed in the Consent Document or this protocol document. Frequent monitoring for adverse effects will help to minimize the risks associated with administration of the study agents.

12.6.6 Questionnaires risks

Questionnaires may contain questions that are sensitive in nature.

12.6.7 Non-Physical Risks of Genetic Research

12.6.7.1 Risk of receiving unwanted information

Anxiety and stress may arise as a result of the anticipation that unwanted information regarding disease related DNA sequencing or disease tendencies, or misattributed paternity. Patients will be clearly informed that the data related to DNA sequencing and genetic analysis is coded, investigational and will not be shared with patients, family members or health care providers.

12.6.7.2 Risk related to possibility that information may be released

This includes the risk that data related to genotype, DNA sequencing or risk for disease tendency or trait can be released to members of the public, insurers, employers, or law enforcement agencies. Although there are no plans to release results to the patients, family members or health care providers, this risk will be included in the informed consent document.

12.6.8 Certificate of Confidentiality

As part of study efforts to provide confidentiality of subject information, this study will obtain a Certificate of Confidentiality which helps to prevent forced disclosure of personally identifiable research information. The Certificate of Confidentiality allows investigators on this trial to refuse to disclose identifying information related to the research participants, should such disclosure have adverse consequences for subjects or damage their financial standing, employability, insurability or reputation. The informed consent includes the appropriate coverage and restrictions of the Certificate of Confidentiality. This study may involve unpredictable risks to the participants.

12.6.9 Potential Benefits

The study drug may help to control the disease. Future patients may benefit from what is learned.

12.7 RISKS/BENEFITS ANALYSIS

This study is for patients who have relapsed from standard therapies for ependymoma. Currently, no

standard therapy at recurrence has been established, and the impact of chemotherapy at recurrence has been limited. Participants may obtain better responses with marizomib.

Please see section [12.2](#) above for the risk benefit analysis for children and viable neonates.

Please see section [12.3](#) above for the risk benefit analysis for nonviable neonates and neonates of uncertain viability.

Please see section [12.4](#) above for the risk benefit analysis for pregnant women.

12.8 CONSENT PROCESS AND DOCUMENTATION

The informed consent document will be provided to the participant or consent designee(s) as applicable for review prior to consenting. A designated study investigator will carefully explain the procedures and tests involved in this study, and the associated risks, discomforts and benefits. In order to minimize potential coercion, as much time as is needed to review the document will be given, including an opportunity to discuss it with friends, family members and/or other advisors, and to ask questions of any designated study investigator. A signed informed consent document will be obtained prior to entry onto the study.

The initial consent process as well as re-consent, when required, may take place in person or remotely (e.g., via telephone or other NIH approved remote platforms) per discretion of the designated study investigator and with the agreement of the participant/consent designee(s). Whether in person or remote, the privacy of the subject will be maintained. Consenting investigators (and participant/consent designee, when in person) will be located in a private area (e.g., clinic consult room). When consent is conducted remotely, the participant/consent designee will be informed of the private nature of the discussion and will be encouraged to relocate to a more private setting if needed.

12.8.1 Consent Process for Adults Who Lack Capacity to Consent to Research Participation

For participants addressed in Section [12.5](#), an LAR will be identified consistent with Policy 403 and informed consent obtained from the LAR, as described in Section [12.8](#).

12.8.2 Consent for Children and Neonates

The consent procedures referenced above will be followed, with both parents involved in the consenting process per Sponsor request. The child's consent will be signed by both parents unless one parent is deceased, unknown, incompetent or not reasonably available, or when only one parent has legal responsibility for the care and custody of the child. When guardianship status of the child is uncertain, documentation of custody status must be obtained.

As information is only collected for up to one year after birth, assent will not be obtained from child participants. While children may be enrolled after the age of 1 year for retroactive data collection if required, given the anticipated duration of the study, no child exposed in utero is expected to have attained the capacity to provide assent while the study is ongoing.

